#### **8.4 Changes in laboratory test values and vital signs**

The protocol requires the collection of the following at Days 0, 1, 3 and 7:

- CBC: White cell count and differential white cell count (neutrophil and lymphocyte percentages), hemoglobin, hematocrit, and platelets.
- Blood chemistries: creatinine, glucose, total protein, ALT/GPT, AST/GOT, total bilirubin.
- Vital signs, including SaO2.
- PT, INR.

- a. Figure and associated Table: For each test: median, 25th and 75th percentiles at each required measurement time (min, max and sample size also in table).
- b. Figure and associated Table: For each test: median, 25th and 75th percentiles change from Day 0 at each required measurement time (min, max and sample size also in table).

Note –laboratory abnormalities that are clinically significant, or require an intervention, are captured as AEs above.

#### **8.5 Pregnancies**

- a. List of pregnancies including: randomized arm, subject ID, site, age of woman, gestational age at first infusion, gestational age at pregnancy outcome, type of outcome, narrative of outcome; infants' birth weight; narrative of complications if any, and presence of pre-term labor. (Sort by randomized arm, subject ID).

### **9. Pharmacokinetic analysis**

- a. Figure and associated table for each strain tested: geometric mean HAI titer with 95% CI on study Days 0, 1, 3 and 7.

- b. Figure and associated table for HAI from infecting strain (H1 or H3): geometric mean HAI titer with 95% CI on study Days 0, 1, 3 and 7.  
*(note – this is the PK from the plasma as well as the natural development of antibodies occurring after an infection)*
- c. Figure and associated table for HAI from non-infecting strain (H1 or H3): geometric mean HAI titer with 95% CI on study Days 0, 1, 3 and 7. *(note – this is the PK from the plasma and should not be significantly affected from development of antibodies to a different strain)*
- d. Figure and associated table for each strain tested: geometric mean HAI titer ratio (versus Day 0 titer) with 95% CI on Days 1, 3 and 7.
- e. Figure and associated table from infecting strain (H1 or H3): geometric mean HAI titer ratio (versus Day 0 titer) with 95% CI on Days 1, 3 and 7.
- f. Figure and associated table from non-infecting strain (H1 or H3): geometric mean HAI titer ratio (versus Day 0 titer) with 95% CI on Days 1, 3 and 7.

## **10. Efficacy Analysis (mITT population)**

### **10.1 Primary endpoint: Clinical status at Day 7**

The primary endpoint is the subject's clinical status at Day 7 on a 6-point ordinal scale:

- 1. death;
- 2. in the ICU;
- 3. non-ICU hospitalization, requiring supplemental oxygen;
- 4. non-ICU hospitalization, not requiring supplemental oxygen;
- 5. not hospitalized, but unable to resume normal activities; or
- 6. not hospitalized with full resumption of normal activities.

- a. Table: Number (%) of subjects in each category of the 6-point scale, showing also number with missing values. Analysis of the primary endpoint will use a proportional odds model with an indicator variable for randomized treatment. The Wald test will be used to generate a p-value comparing treatments, as well as the estimated proportional odds ratio comparing treatments with associated 95% CI. A sensitivity analysis will be undertaken using the score test (the score test of the treatment effect from a proportional odds model is equivalent to a Wilcoxon rank sum test even if the proportional odds assumption does not hold). If there are missing data for the primary endpoint, then a sensitivity analysis will be undertaken to evaluate the sensitivity of study conclusions to the handling of the missing data using the last known status of the subject. A sensitivity analysis will be performed using the ITT population. The proportional odds model will be extended to undertake comparison of randomized treatments adjusted for the clinical status at baseline (this will use two indicator variables to reflect the three possible categories at baseline [categories 2, 3 and 4 in the list above]); other adjusted analyses may also be taken for any baseline variables about which there might be concern about an imbalance at baseline.
- b. Subgroup analyses: For each subgroup variable a table will be generated showing the number (%) of subjects in each category of the 6-point scale and the number with missing values for each level of the subgroup variable. The proportional odds model will be extended to evaluate

possible differences in the comparison of randomized treatments between subgroups of subjects (including subgroup indicator variable(s) for the main effect and indicator variables(s) for the treatment by subgroup interaction). The following subgroup variables are pre-specified for analysis: sex (male/female), age (adult/child), race/ethnicity (based on IRC 002, this is anticipated to be white/black/other), clinical status at baseline (the three possible categories), NEW/PEW score at baseline (categorized as above/below median separately for adults and children), and days since onset of influenza symptoms to randomization ( $\leq 4$  versus 5-6).

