5.2 Randomization

Subjects who meet all criteria for enrollment will be randomized using an interactive web response system (IWRS) to receive high-titer anti-influenza plasma or low-titer plasma in a 2:1 ratio. A central randomization scheme has been prepared by the sponsor. Randomization is stratified by:

- Severity: in the ICU, non-ICU hospitalization requiring supplemental oxygen, or non-ICU hospitalization not requiring supplemental oxygen
- Age category (child/adult)

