10.8 Data and Safety Monitoring Plan

The NIAID Intramural DSMB includes independent experts that do not have direct involvement in the conduct of the study and have no significant conflicts of interests as defined by NIAID policy. The Board reviewed the study prior to initiation and will review the study yearly thereafter, unless otherwise recommended by the Board. Given the seasonal nature of influenza (generally November through April) the interim reviews will occur after each influenza season. The Board may convene additional reviews as necessary. The Board will review the study data to evaluate the safety, efficacy, study progress, and conduct of the study. All SAEs, all UPs, and all IND Safety Reports will be reported to the DSMB by the CSO. The DSMB will be notified of any cases of intentional or unintentional unblinding as soon as possible.

As a guideline for monitoring results comparing randomized treatments for the primary endpoint, as it is unlikely that this trial will be replicated, a high level of evidence concerning any favorable effect of high-titer versus low-titer anti-influenza plasma is considered desirable before considering early termination of the study. For this reason, the Peto-Haybittle stopping guideline will be used; this requires a nominal p-value of < 0.001 at an interim analysis in order for termination to be considered. Such a level of evidence would also facilitate more precise comparison of effects in patient subgroups and for secondary endpoints. Although application of this guideline is focused on the primary endpoint, if a similar level of evidence is achieved first in comparing mortality rates between randomized arms, then termination of the study might also be considered.

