Based on the above assumptions, the table also shows the type of true difference (assuming proportional odds) that would be detected with 80% or 90% power. For example, the study would have 80% power to detect a proportional odds ratio of 2.50. This is the odds ratio that arises when comparing the proportion not hospitalized and able to resume normal activities in the high-titer arm (30.6%) to that in the low-titer arm (15%). The proportional odds model assumes that the same odds ratio applies to the cumulative proportions moving up the ordinal scale: for example, for the proportion not hospitalized in the high-titer arm ($30.6+7.9=38.5\%$) to that in the low-titer arm ($15+5=20\%$); or for the proportion alive and not in an ICU in the high-titer arm ($30.6+7.9+13.3+23.6=75.4\%$) to that in the low-titer arm ($15+5+10+25=55\%$).

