12.3 Statistical Analysis

A detailed statistical analysis plan will be developed before undertaking any comparative analyses of outcomes for the randomized high and low plasma titers. The following provides a brief summary of approach to analysis for the primary endpoint.

As noted above, the primary analysis will use a modified intention-to-treat approach which excludes randomized subjects who do not have an infusion of study plasma started. Statistical inferences will use a two-sided Type 1 error rate of 0.05, and corresponding 95% confidence intervals.

Analysis of the primary endpoint (ordinal outcome of clinical status at Day 7) will use a proportional odds model with an indicator variable for randomized treatment. It is useful to note that the score test of the treatment effect from a proportional odds model is equivalent to a Wilcoxon rank sum test even if the proportional odds assumption does not hold. If there are missing data for the primary endpoint, then sensitivity analyses will be undertaken to evaluate the sensitivity of study conclusions to the handling of the missing data. The proportional odds model will be extended to undertake comparisons of randomized treatments adjusted for variables that might be predictive of the outcome, for example, the ordinal clinical status at baseline. The model will also be extended to evaluate possible differences in the comparison of randomized treatments between subgroups of subjects (treatment by subgroup interaction), including subgroups defined by sex, age (adult/child), race/ethnicity, ordinal clinical status at baseline, NEW score at baseline, and days since onset of influenza symptoms to randomization.

Binary variables such as 28-day mortality, in-hospital mortality, incidence of new ICU admissions, etc., are expected to occur infrequently and will be compared between randomized arms using exact logistic regression. Quantitative variables such as duration of ICU stay and change from baseline in NEW score, etc., are expected to have reasonably skewed distributions and may be subject to censoring (e.g., for subjects in an ICU on Day 28); these will be compared between randomized arms using non-parametric tests (e.g., Wilcoxon's Test adapted, if necessary, to handle censoring).

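### The primary Day 7 model leaves out the severity stratifier; making the already planned severity-adjusted model primary would gain power at little cost

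*SAP*

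**What the plan says.** Protocol 5.2 stratifies randomization by two factors. One is "Severity: in the ICU, non-ICU hospitalization requiring supplemental oxygen, or non-ICU hospitalization not requiring supplemental oxygen"; the other is child/adult. The three severity levels are categories 2, 3 and 4 of the Day 7 outcome scale.

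The primary analysis uses neither factor. Protocol 12.3 "will use a proportional odds model with an indicator variable for randomized treatment". SAP 10.1a repeats this, "Analysis of the primary endpoint will use a proportional odds model with an indicator variable for randomized treatment", and takes the p-value from the Wald test. The score test is a sensitivity analysis, on the ground that it "is equivalent to a Wilcoxon rank sum test even if the proportional odds assumption does not hold".

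SAP 10.1a then extends the model to a comparison "adjusted for the clinical status at baseline (this will use two indicator variables to reflect the three possible categories at baseline". So the severity-adjusted model is fully specified, but not as primary. Protocol 12.3 itself names baseline clinical status as a possible predictor of outcome.

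The design claim in Protocol 12.2 is that "the study would have 80% power to detect a proportional odds ratio of 2.50", and 90% power at 2.88, with 135 effective subjects. For early stopping, Protocol 10.8 says of its guideline that "this requires a nominal p-value of < 0.001 at an interim analysis in order for termination to be considered", applied to the primary endpoint.

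**The concern.** Stratified randomization removes part of the between-arm variation in outcome. A treatment-only model does not know this. If severity is prognostic and allocation is balanced within strata, the model's standard error exceeds the true sampling variability, and a nominal 5% test rejects less than 5% of the time under the null. The trial would then lose power for which it has already collected the data. Protocol 10.8 considers replication of the trial unlikely, which makes the loss worth avoiding. What is at stake is efficiency. Validity is not in doubt.

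**Working it through.** **1. The plan's own power.** Inputs from Protocol 12.2: N = 135, allocation ratio A = 2, two-sided 5%, Table 12 distributions. Whitehead's formula:

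V = N·A / [3(A+1)²] × (1 − Σp̄³), power = Φ(ln OR × √V − 1.96), where p̄ is the average of the two arms in each category.

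The first factor is 135 × 2 / 27 = 10.

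- OR 2.50: Σp̄³ = 0.0497, V = 9.50, power = Φ(0.916 × 3.083 − 1.96) = Φ(0.865) = 80.6%.
- OR 2.88: Σp̄³ = 0.0492, V = 9.51, power = Φ(1.058 × 3.084 − 1.96) = Φ(1.302) = 90.3%.

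Both stated figures reproduce.

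**2. Simulation of the two models.** There were 20,000 trials per cell with N = 135, 2:1 allocation, the Table 12 control distribution and Wald tests. The following are assumptions:

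- Permuted blocks of 3 within the six strata.
- Baseline mix ICU / oxygen / no oxygen of 58 / 24 / 18%. In IRC002 58% were in ICU and 82% needed oxygen; taking all ICU patients as on oxygen gives 82 − 58 = 24% and 100 − 82 = 18%.
- 11% children (11 of 98 in IRC002), with child odds ratio 2 (1 when severity is not prognostic).
- Odds ratio per severity step of 1, 1.6, 2.7 or 4.5. The documents give no value.

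The conditional odds ratio was set so that the marginal proportional odds fit is 2.50 or 2.88. Monte Carlo error is about 0.15 points on type I error and 0.3 on power.

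| OR per severity step | 1 | 1.6 | 2.7 | 4.5 |
|---|---|---|---|---|
| Type I error %, treatment-only | 5.2 | 4.3 | 3.4 | 2.0 |
| Type I error %, severity-adjusted | 5.4 | 5.0 | 5.3 | 5.0 |
| Power % at 2.50, treatment-only | 79.6 | 80.8 | 81.8 | 83.0 |
| Power % at 2.50, adjusted | 80.1 | 82.5 | 87.2 | 91.8 |
| Gain, points (from unrounded values) | 0.5 | 1.8 | 5.4 | 8.8 |
| Power % at 2.88, treatment-only | 89.9 | 90.8 | 92.0 | 93.0 |
| Power % at 2.88, adjusted | 90.1 | 91.8 | 94.7 | 97.2 |
| Power % at 2.50, size exactly 5%, treatment-only | 79.1 | 82.4 | 85.9 | 90.5 |
| Power % at 2.50, size exactly 5%, adjusted | 79.0 | 82.6 | 86.6 | 91.8 |

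**3. The mechanism.** At step 2.7 and OR 2.50 the treatment-only standard error averages 0.336 against a true SD of 0.316, so it is 6% too large (0.336 / 0.316 = 1.06). The adjusted model's is 0.343 against 0.350. Its coefficient is larger (conditional OR 2.80), so the estimate over its standard error rises from ln 2.50 / 0.336 = 2.73 to ln 2.80 / 0.343 = 3.00.

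**4. Sensitivity at step 2.7** (treatment-only v adjusted; 10,000 trials unless stated).

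| Change | Type I error % | Power % at 2.50 |
|---|---|---|
| Blocks of 6 | 3.5 v 5.1 | 81.9 v 87.2 |
| Child odds ratio 1 | 3.4 v 5.4 | 81.7 v 86.9 |
| Non-proportional severity effect | 2.9 v 4.6 | 82.4 v 87.0 |
| Mix 35 / 40 / 25% | 3.4 v 5.2 | 81.3 v 86.6 |
| 150 randomized, 15 dropped at random (error on size about 0.3) | 3.8 v 5.4 | 81.6 v 87.0 |
| Allocation not balanced within strata | 5.5 v 5.5 | 79.3 v 85.5 |

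The conservatism needs balance within strata. The power gain does not.

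A separate set of runs used a 50 / 35 / 15% mix, blocks of 6 and 2,000 to 4,000 trials per cell. With log-odds of 1 and 1.5 above ICU, treatment-only size was 3.4% and power rose from 80% to 84%. With 1.5 and 2.5, size was 2.3% and power rose from 83% to 90%.

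**5. What IRC002 says about prognosis.** The 58% in ICU at baseline fits 57 of 98. Eleven subjects lie outside the 87 in Table 3, and 24 + 31 = 55 of the 87 were ever in ICU, so 46 to 55 of the 87 were in ICU at baseline. If 50 were, at most 55 − 50 = 5 entered later, so at least 22 of the 27 in ICU at Day 7 were there at baseline. Placing all 5 deaths among the other 37 subjects gives the minimum odds ratio for ICU or death: (22/28) / (10/27) = 2.1. The minimum is 1.2 at 46 and 5.2 at 55, with no finite upper limit. Steps 1.6 / 2.7 / 4.5 imply 1.9 / 3.9 / 7.2, so IRC002 does not locate the step.

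**6. Interim guideline.** At an assumed look at 100 subjects and OR 2.50, the chance of p < 0.001 is 16.9 / 15.9 / 14.7 / 13.1% treatment-only and 17.9 / 18.6 / 23.6 / 32.0% adjusted. Under the null it is 0.03–0.09% and 0.08–0.13%.

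**The case against.** The plan has no defect here. Protocol and SAP agree, the test is valid, the stated power is met, and the adjusted analysis will be reported anyway; only the label changes. That stands, and it is why this is an optional improvement.

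The gain rests on values that are not in the documents. The 8.8 points come from a step of 4.5, an odds ratio of about 20 (4.5²) between ICU and no-oxygen patients, and at equal size the gain is at most 1.3 points. That stands too. But the plan uses a nominal Wald test, so type I error left unused is a real loss.

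The adjusted test runs at or slightly above 5%: 5.0–5.4% in the main runs, and 6.3% in one run of only 2,000 trials. A mildly conservative test also suits a protocol that asks for strong evidence, and easier crossing at an interim look is not plainly a benefit. This supports keeping the treatment-only and rank tests beside the adjusted one.

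The interim ambiguity does not exist today, because there is one primary model; it would arise only from the change. Agreed, so the change must settle it.

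The endpoint was harmonized with the FLU-IVIG study, and a conditional odds ratio depends on covariates and case mix. Reporting the marginal odds ratio as well preserves the comparison.

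The other outcome days in SAP 10.2a were not computed. Using the same covariates there is for consistency and has no demonstrated gain.

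**Conclusion.** The point holds as an improvement to a valid plan. Making the severity-adjusted model primary gains between about nothing and 9 points of power at OR 2.50 (0.2 to 4.2 points at 2.88) with the same patients. Where the trial falls in that range depends on how strongly baseline severity predicts Day 7 status, which the documents do not show. Most of the gain is type I error that the treatment-only test leaves unused when allocation is balanced within strata. If severity matters little, almost nothing changes. The direction and approximate size held across the block sizes, baseline mixes, non-proportional severity effect and random exclusions tried.

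**What to change.** In SAP 10.1a and Protocol 12.3, make the model with treatment and the two baseline status indicators primary. Child/adult may be added as a main effect for consistency with the stratification; it adds 0.1 to 0.5 points of power and brings type I error to 5.2–5.6%.

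Keep the treatment-only Wald test and the Wilcoxon/score test as sensitivity analyses. Add a severity-stratified Wilcoxon (van Elteren) test as the matching rank test; its type I error is 5.1 / 4.6 / 5.0 / 4.6% and its power at OR 2.50 is 78.9 / 81.6 / 86.3 / 91.2%. Report the marginal odds ratio beside the conditional one, and use the same covariates in SAP 10.2a. In Protocol 10.8, say that the adjusted model also serves the p < 0.001 guideline, and whether conditional power uses the marginal odds ratio of Table 12 (2.88) or its conditional counterpart.

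The cost is wording in four sections and no new data. The primary odds ratio becomes conditional: 2.58 / 2.80 / 3.14 for marginal 2.50, and 2.99 / 3.28 / 3.75 for 2.88, at steps 1.6 / 2.7 / 4.5. It no longer matches Table 12, and the exact Wilcoxon equivalence is lost for the primary model. Protocol 12.3 promises that "A detailed statistical analysis plan will be developed before undertaking any comparative analyses of outcomes", but enrolment has begun (Protocol 8.1.1 reports an IRC005 event) and the DSMB reviews after each season. The change must therefore be made by people blind to comparative results, and the DSMB told which model its efficacy reports use.

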## **10.2 Secondary endpoints: Clinical status outcomes**

- a. Table of ordinal outcome during follow-up: Number (%) of subjects in each category of the 6-point scale on each study Day, showing also number with missing values (for completeness the table will also show the status at Day 0 and Day 7). At each study Day, the table will also show the p-value comparing treatments (Wald test from the proportional odds model), as well as the estimated proportional odds ratio comparing treatments with associated 95% CI. A sensitivity analysis will be performed using the ITT population.
- b. Table of composite of mortality and hospitalization: Number (%) of subjects died prior to, or still in hospital on each of Days 7, 14 and 28, showing also number with missing values due to loss to follow-up. At each study Day, the table will also show the p-value comparing treatments (Wald test from a logistic regression model) as well as the estimated odds ratio comparing treatments with associated 95% CI.

## **10.3 Disposition**

- a. Table of disposition following initial hospitalization (home without assistance, home with home health care, rehabilitation, chronic nursing facility, initial hospitalization ongoing at 28 days, died during initial hospitalization): Number (%) of subjects in each disposition category, showing also number with missing values (eg due to withdrawal of consent during initial hospitalization). The table will also show the p-value comparing treatments (Wald test from the proportional odds model), as well as the estimated proportional odds ratio comparing treatments with associated 95% CI.

## **10.4 Secondary endpoints: Hospitalization, intensive care/support and ARDS**

The protocol specifies the following secondary endpoints:

- Duration of initial hospitalization
- Duration of all hospitalizations
- Duration of admission to an ICU among those in an ICU at randomization
- Incidence of new ICU admission among those not in an ICU at randomization
- Duration of supplemental oxygen use among those requiring oxygen at randomization
- Incidence of supplemental oxygen use among those not requiring oxygen at randomization
- Duration of mechanical ventilation use among those requiring mechanical ventilation at randomization
- Incidence of new mechanical ventilation use among those not requiring mechanical ventilation at randomization

- Duration of ECMO use among those on ECMO at randomization
- Incidence of new ECMO use among those not on ECMO at randomization
- Duration of ARDS among those with ARDS at randomization
- Incidence of new ARDS among those not having ARDS at randomization

Notes:

- i. Each of these measures will be evaluated through to the Day 28 visit and so will reflect the use of interventions (or of ARDS) during the study follow-up period.
- ii. Deaths and losses to follow-up may affect the interpretation of the results for these endpoints (e.g. deaths, losses to follow-up). Sensitivity analyses may be undertaken to assess how the interpretation of formal analyses might be affected by these issues.

- a. Table showing durations of interventions: n (will be overall sample size for hospitalizations, and number receiving intervention at randomization for other interventions and ARDS), median, 25th and 75th percentiles and min, max. Difference in medians between treatments, p-value from Wilcoxon's test and associated 95% CI for difference.
- b. Table showing incident use of intervention (or new development of ARDS): n (will be number not receiving intervention or not having ARDS at randomization), number (%) with incident use of intervention (or new development of ARDS), difference in %'s between treatments, and odds ratio comparing treatments with p-value and associated 95% CI from exact logistic regression.

